7.3 Baseline Definition

The baseline for this study is defined as the last assessment prior to the first treatment infusion. The exception to this rule is cardiac MRI. Due to a different scheduling of cardiac MRI and, in some cases, repeated cardiac MRI due to inability to interpret it, delayed baseline cardiac MRI, with a delay of up to 60 days will be considered as baseline (Perry et al, 2019).

7.4 Subgroup Analysis

Subgroup analyses will be conducted based on baseline characteristics and demographics for selected efficacy and safety endpoints and only if the size of each of the groups is at least 10 (combined over the two treatment arms). If a patient is missing a value at baseline for one or more of the subgroups, the classification will be based on the value at screening.

Whether a subgroup analysis will be conducted for a specific endpoint, and if yes for which of the subgroups the analysis will be done, will be discussed in the analysis section of the specific endpoint. The selection of subgroup will be from the following list:

- Gender (Male or Female)
- Anti-Drug Antibodies (ADA) status at baseline (Negative; Positive). Determination of status is based on Immunoglobulin G (IgG) positive at baseline (Section 11.7). For patients who were randomized to PRX-102 arm, their ADA status at for PRX-102 at baseline will be used. For patients who were randomized to agalsidase-beta arm, their ADA status at for agalsidase-beta at baseline will be used. In case the test for baseline visit is missing, then the result from the screening visit will be used.
- FD classification (Classic/Non-Classic). In order to be classified as FD classic, a patient should have $\leq 5\%$ mean of lab normal ranges residual enzymatic activity in plasma or leukocytes at baseline visit and at least one Fabry specific symptom: Cornea Verticillata, Acroparesthesias, Angiokeratomas. Evaluation of Fabry specific sympom is based on the Fabry Disease Medical History collected at screening visit. Mean normal range is defined as (lower limit of normal + upper limit of normal)/2) and % of mean of lab normal range is defined as (100 × test result / mean normal range); this was calculated within the EDC system and will not be re-derived for the purpose of the analysis. In case of missing information for the symptoms or residual activity, which does not allow for clear classification as classic or non-classic, the FD classification will be missing and the subject will be excluded from the sub-group analysis (for example, if a patient meets the symptoms requirement and have a plasma residual activity of 10% but the leukocytes residual activity is missing then the classification will be missing and the patient will be excluded from the subgroup analysis. As another example, if a patient meets the symptoms requirement and have a plasma residual activity of 3% and the leukocytes residual activity is missing, it is still possible to classify the patient as Classic and the patient will be included in the subgroup analysis).
- Baseline eGFR (≤ 60 ; $60 < \text{and} \leq 90$; $> 90 \text{ mL/min/}1.73\text{m}^2$)
- Annualized slope of eGFR (\leq -5; > -5 mL/min/1.73m²/year)
- Use of ACEi or ARB treatment at baseline (Yes/No). The usage of ACEi or ARB is based on classification in the medication form in the eCRF. Based on this form, it is possible to identify

patients who received ACEi or ARB at Baseline date. All other patients will be classified as "No" for this subgroup.

- Region (United States (US)/ex-US)
- UPCR categories ($\leq 0.5 \text{ gr/gr}$; 0.5 < and < 1 gr/gr; $\geq 1 \text{ gr/gr}$).

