3.1 Sample Size and Statistical Power Consideration

The section below is based on the plan at the time of the protocol and does not reflect the change in the planned analysis for the final analysis. The number of patients randomized was 78, as planned.

This orphan indication allows for a small number of patients, given the rarity of the disease and the difficulties in allocating patients for clinical trials. Two tests are planned to be performed as part of the primary efficacy analysis for this protocol. The first test, to test the non-inferiority hypothesis, will be performed using data collected after the last patient have at least 12 months of treatment (interim analysis). The second test, to test the superiority hypothesis, will occur with the data from 24 months of treatment (final analysis). We now describe the statistical power/sample size considerations for these two tests.

Sample Size and Power for the Non-Inferiority Analysis (Interim Analysis)

With a total of approximately 66 patients in 2:1 randomization ratio there is at least 90% power to demonstrate the non-inferiority of PRX-102 vs. agalsidase beta in terms of mean annualized change (slope) in eGFR. The power is computed assuming one-sided two-sample t-test with a one-sided alpha level of 0.025 and the non-inferiority margin of -3.0 mL/min/1.73 m²/year. The true difference in slopes is assumed to be 1.1 mL/min/1.73 m²/year in favor of PRX-102 and the standard deviation of the slopes being 1.5 mL/min/1.73 m²/year in each group.

Sample Size and Power for the Superiority Analysis (Final Analysis)

With a total of approximately 66 patients in 2:1 randomization ratio there is approximately 80% power to detect a difference of 1.1 mL/min/1.73 m²/year between the mean annualized change (slope) in the two arms. The power is computed assuming two-sample t-test at two-sided alpha level of 0.05 and the standard deviation of the slopes being 1.5 mL/min/1.73 m²/year in each group.

For this analysis the null hypothesis is that the difference in mean annualized change in eGFR between the treatment groups is 0 versus an alternative hypothesis that it is not 0.

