Based on previous research, the mean annualized change (slope) in eGFR in patients treated with agalsidase beta is -3.0 mL/min/1.73 m²/year. A 1.1 reduction in the rate of decline in renal function (improvement) is anticipated to be equal to a mean annualized change (slope) in eGFR with PRX-102 of -1.9 mL/min/1.73 m²/year representing an approximately 30% improvement, which would be considered a clinically relevant improvement.

To allow for a drop-out rate as large as 15%, approximately 78 patients will be randomized. Approximately 52 patients will be randomized to PRX-102 and approximately 26 patients will be randomized to agalsidase beta to have approximately 44 and 22 completers in the PRX-102 and agalsidase beta arms, respectively.

These power calculations are based on two-sample t-test and were performed using PASS-13 Tests for Two Means procedure (Hintze, 2014).

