3.2 Randomization

Patients will be randomized in 2:1 ratio to PRX-102 and agalsidase beta. Randomization will be stratified by urinary protein to creatinine ratio (UPCR) of < or ≥ 1 gr/gr (1 mg/mg or 1000 mg/g) by spot urine sample.

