9.6 Subgroups

The analyses described in this section will be conducted on the ITT set.

Descriptive statistics of eGFR values and the change from Baseline will be summarized by visit and treatment arm for all subgroups defined in Section 7.4.

The statistical approach used for the primary analysis (Section 9.2) will be repeated for all these sub-groups.

For each of the subgroups, the primary model (i.e., two-stage with quantile regression) will be used for each level of the subgroup separately with the same covariates as the primary model. A 95% CI for the treatment effect within each level of a subgroup will be presented.

The results will be presented graphically by a forest plot.

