10.2 Plasma Lyso-Gb3 Concentrations

Descriptive statistics of plasma Lyso-Gb3 concentration (nM) will be summarized at each visit. The change and percent change from Baseline will be summarized as well.

A MMRM approach will be used to model the change from baseline of log of plasma Lyso-Gb3. The outcome will consist of the change from baseline of log of Lyso-Gb3 at each post baseline visit. The variables to be included in the model are log plasma Lyso-Gb3 at Baseline, visit (class variable), treatment (class variable), visit by treatment interaction term.

The first choice for the within-patient correlations will be an unstructured covariance structure. If the model does not converge, the model will be fitted assuming a heterogeneous Toeplitz structure, followed by a homogeneous Toeplitz structure, and then a compound symmetry structure until a stable model is achieved. Only data at scheduled visits will be used for this analysis. Missing data will not be imputed. The Kenward-Roger degrees of freedom approximation will be used. Appendix A.2 (Section 17) provides details and pseudo-SAS code for this analysis.

95% CI for the contrast between treatment arms at 1-year visit (Week 52) and at the 2-year visit (Week 104) will be presented, as well as the two-sided p-value for the null hypothesis of no difference between the two arms. Adjusted LSMEANS of the two treatment arms for the change from Baseline to 1-year and from Baseline to 2-year will be presented along with a 95% CI.

The analysis will be repeated for the following subgroups: ADA status, gender and FD classification. A 95% CI for the treatment effect within each level of a subgroup will be presented.

The mean \pm SE of plasma Lyso-Gb3 and the change from baseline over time will be presented graphically by treatment group and by gender.

The number and percentage of patients who improved by at least 30%, 40% and 50% will be summarized at Week 52 and at Week 104 by treatment arm and for the above sub-groups.

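### SAP 7.4 admits a subgroup level on 10 patients over both arms with no per-arm minimum, so a planned 95% CI can rest on one or two controls and look falsely precise (minor)

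*SAP*

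**What the plan says.** SAP 7.4 sets one size condition for subgroup analyses: they are done "only if the size of each of the groups is at least 10 (combined over the two treatment arms"). Neither 7.4 nor 9.6 sets a minimum per arm. The rule also does not say whether the 10 are patients or patients with evaluable data.

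For the primary endpoint, SAP 9.6 applies the two-stage median regression to all the 7.4 subgroups. The model "will be used for each level of the subgroup separately", and "A 95% CI for the treatment effect within each level of a subgroup will be presented", with a forest plot. SAP 17.5 specifies resampling for the standard error. Under SAP 9.2, a patient with fewer than 4 eGFR values has no slope.

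For plasma Lyso-Gb3, SAP 10.2 states: "The analysis will be repeated for the following subgroups: ADA status, gender and FD classification". It again calls for a 95% CI within each level.

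On allocation, SAP 3.2 states: "Patients will be randomized in 2:1 ratio to PRX-102 and agalsidase beta". UPCR, cut at 1 gr/gr, is the only stratification factor. SAP 3.1 reports that "The number of patients randomized was 78, as planned", and plans about 52 and 26 per arm.

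SAP 7.6.2 makes subgroup results nominal, without claims of significance.

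**The concern.** A between-arm contrast is limited by its smaller arm, and the rule counts both arms together. At 2:1, a level can pass with very few controls, or with none, in which case no difference can be estimated. Only the UPCR cut at 1 gr/gr is stratified, so the other subgroup factors have no built-in balance.

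The danger is less a wide interval, which warns the reader, than one that is too narrow. With one control, resampling within that arm returns the same value each time, so the arm contributes no variance. The level with least information can then show one of the tighter intervals in the forest plot, labelled 95%. What is at stake is how the subgroup display is read.

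**Working it through.** **Inputs.** 78 randomised, planned 52 PRX-102 and 26 agalsidase beta (SAP 3.1); threshold of 10 combined (SAP 7.4); slope SD 1.5 mL/min/1.73 m²/year per arm (SAP 3.1); resampling CI (SAP 17.5).

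**The plan's own figure.** The documents give no power or precision figure for subgroups. The nearest is the whole-trial superiority power of about 80%. SE = 1.5 × √(1/44 + 1/22) = 0.392; 1.1/0.392 = 2.81; Φ(2.81 − 1.96) ≈ 0.80. It reproduces by the normal approximation, so the inputs are read as the plan used them.

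**Controls in a level of n patients.** Expected number = n/3, so 10/3 = 3.33. If membership is unrelated to arm, the count is hypergeometric: P(k) = C(26,k) × C(52,n−k) / C(78,n). For n = 10: P(0) = 0.0126, P(1) = 0.0760, P(2) = 0.1944; the sum is 0.283.

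| Level size | Expected controls | P(2 or fewer) | P(1 or none) | P(none) |
|---|---|---|---|---|
| 10 | 3.3 | 28.3% | 8.9% | 1.3% |
| 12 | 4.0 | 15.9% | 4.1% | 0.5% |
| 15 | 5.0 | 5.9% | 1.2% | 0.1% |
| 20 | 6.7 | 0.8% | 0.1% | <0.1% |

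**Illustrative coverage.** Normal slopes, SD 1.5 in both arms, no true difference. Patients are resampled separately within each arm, and the interval is the median difference ± t(0.975, n − 2) × bootstrap SE. Ranges are over two runs of 3,000 and 10,000 replicates.

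| PRX-102 : control | Coverage of nominal 95% CI | Median full width |
|---|---|---|
| 9:1 | 62–64% | 2.9 |
| 8:2 | 86–87% | 4.0–4.1 |
| 7:3 | 96% | 5.6 |
| 44:22 | 95% | 2.0 |

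At 6:4 and 5:5, coverage was 96 to 98%. The method is therefore sound at full size and near nominal from 3 controls, and it fails at 1 or 2. Within a level of 10, width moves the wrong way: 9:1 is the narrowest and covers least.

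**If whole patients were resampled across arms instead.** The chance that a resample contains no control is 0.9^10 = 35% at 9:1, 0.8^10 = 11% at 8:2 and 0.7^10 = 3% at 7:3. That scheme also strains at 1 or 2 controls.

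**The case against.** The strongest reply is that the problem is hypothetical and already contained. No subgroup sizes appear in the documents. The rule can be read as dropping a whole subgroup factor when any one level falls short. The risk fades quickly above 10 patients, and SAP 7.6.2 bars claims of significance. All of that stands and keeps the point minor. It does not remove the gap: under either reading no arm has a minimum, and a disclaimer about significance does not make an interval labelled 95% cover 95%.

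Four stronger readings are tempting, and the documents do not support them.

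- *Any level with 5 or fewer controls is invalid, so about 94% of 10-patient levels fail.* A distribution-free order-statistic interval for a single median does need 6 observations to reach 95% (1 − 2 × 0.5^5 = 93.75%; 1 − 2 × 0.5^6 = 96.9%). The SAP does not use that interval. It uses a resampling SE for a two-arm contrast, for which illustrative coverage is adequate at 3, 4 and 5 controls. A minimum of 6 would also drop 39% of 18-patient levels.
- *Intervals at 7:3 are almost four times the margin.* A width near 11 needs an SD of 3. At the planning SD of 1.5 the full width is about 5.6, so the half-width is 2.8, below 3.0. SAP 9.6 does not test subgroups against the margin.
- *The Lyso-Gb3 subgroup model cannot be fitted.* SAP 10.2 falls back to simpler covariance structures if the unstructured fit does not converge, and the code in SAP 17.7 fits one covariance for both arms. The missing per-arm minimum applies there too, but failure is not shown.
- *Readers would take noise for heterogeneity.* A wide interval signals imprecision. The case that could mislead is the falsely narrow one.

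**Conclusion.** The concern holds in a limited form. SAP 7.4 can admit a level whose between-arm interval is undercovered (1 or 2 controls) or inestimable (none). At exactly 10 patients the chance of 2 or fewer controls is 28%; at 15 it is 6%, and at 20 about 1%.

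This rests on three assumptions. First, membership is unrelated to arm. That is doubtful for ADA status, which SAP 7.4 defines by antibodies to the assigned drug; the imbalance could go either way. Second, the coverages assume normal slopes with equal SD. Third, they come from a within-arm bootstrap; SAP 17.5 does not specify the resampling scheme, and the SAS algorithm may behave differently. Missing slopes could lower the analysed counts further.

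Severity is minor. The consequence is confined to reading nominal subgroup results.

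**What to change.** Add to SAP 7.4: between-arm estimates and CIs for a subgroup level are given only if each arm has at least 3 patients with evaluable data for that endpoint (for 9.6, an estimable slope); other levels are summarised descriptively and marked as such in the forest plot; the number per arm is printed beside every subgroup CI. The rule then covers 9.6, 10.2 and the other subgroup CIs. Three is the smallest control count at which illustrative coverage was near nominal.

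The cost is one sentence and the loss of a CI in a few very small levels. The SAP Introduction commits to removing none of the interim analyses. Any such CI shown at the interim should therefore stay as a descriptive summary, with a note in Section 13.2. SAP Section 1 has the SAP finalised before the final database lock, so the change belongs there.

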7.5 Interim Analysis and Unblinding

The interim analysis was conducted after the last patient randomized completed 12 months of treatment. The primary objective was to demonstrate the non-inferiority of PRX-102 compared to agalsidase beta. The interim analysis was used for submitting an MAA to the EMA, so all other efficacy and safety analyses have been performed at this point and CSR has been written.

The objective of the interim analysis was to support submission of the MAA, with only some individuals at the Sponsor being unblinded at this point to treatment assignment. To protect the blinding of the final analysis, an unblinded data access plan describing the measures to be taken to ensure the blinding of the interim study results and patients' treatment assignments is discussed in Appendix A.1 of this SAP (Section 16). Due to the additional discussions and agreements with the FDA following the full approval of agalsidase beta, some changes had to made to this plan.

7.5.1 Merging Randomization Codes with Clinical Data

Study Data Tabulation Model (SDTM) programming is performed by the Data Management vendor of the study who remains blinded until final analysis, and hence were not able to merge the randomization codes with the clinical data as part of the interim analysis SDTM.

For the interim analysis, merging of the randomization codes was performed by the unblinded team of the vendor that provides statistical analysis services. For consistency the same process will be followed for the final analysis.

7.6 Multiplicity Considerations

7.6.1 Primary Endpoints – Interim and Final Analyses

The primary efficacy endpoint for both interim and final analyses is the mean annualized change (slope) in estimated glomerular filtration rate (eGFR). Both evaluate non-inferiority analysis and the assessment is done using a one-sided alpha level of 0.025.

For regulatory purposes, demonstration of non-inferiority of PRX-102 compared to agalsidase beta at 12 months for submission of MAA to the European Medicines Agency and non-inferiority at 24 months for FDA BLA submission will be considered trial success.

Since there is no intention to stop the study for futility or efficacy and no plan for study adaptations based on outcomes of the interim analysis, no alpha penalty for the final superiority analysis is needed.

7.6.2 Other Efficacy Endpoints

No multiplicity adjustment will be made to other efficacy endpoints or other time-points, sensitivity/supportive analyses, and sub-group analyses. In all these cases, nominal significance will be reported but no claims for significance will be made.

8. DEMOGRAPHICS AND STUDY SUMMARY

8.1 Patient Disposition

The number and percentage of patients who were screened, randomized, completed 12 months of treatment (i.e.: subjects who reached the 12 months study milestone, completed 24 months (i.e.: subjects who have completed the study as per protocol), and discontinued will be summarized by treatment group and overall. The documented reasons for screen failures will be tabulated. The number and percentage of patients who discontinued will also be summarized for each reason of the discontinuation. The number of patients with study prolongation due to COVID-19 will be summarized. In addition, patients who discontinued will be classified based on their time of discontinuation (before or after the interim analysis) and the number and percentage of patients in each of these two categories will be presented.

The number of patients in each of the analysis sets (ITT, Safety and PP) will be summarized by treatment group and overall. For each patient, the reason for exclusion from analysis population will be detailed in listing. The reasons for exclusion from the PP set will be summarized by treatment arm.

Protocol deviations were classified in a blinded manner as minor, major and critical (critical are considered more severe than major and are reserved mainly for Good Clinical Practice violations). A summary table will show the number of subjects with at least one major or critical deviations as well as with breakdown by violation type. All protocol deviations will be listed. The listing will include also violations related to COVID-19 (e.g., visits out of windows).

Time to discontinuation will be presented graphically by Kaplan-Meier (KM), where time will be from 1st infusion. For subjects who completed the study, the time should be censored at the date of last infusion.

To assess the impact of COVID-19, the compliance with infusions and blood collection for eGFR will be summarized descriptively and listed. The compliance will be calculated by the number of actual infusions/blood samples divided by the number of planned infusions/blood samples after March 1st, 2020. The analysis will be conducted only for patients who were still ongoing as of March 1st, 2020.

8.2 Demographics

The demographics (age (calculated using intck function in SAS), gender, race, and ethnicity) will be summarized using descriptive statistics by treatment group, overall, and for each of the subgroups in Section 7.4. This analysis will be done on the ITT set.

8.3 Baseline Characteristics

The following baseline characteristics will be summarized on the ITT analysis set by descriptive statistics by treatment group, overall and for each of the subgroups in Section 7.4:

- Weight
- Height
- Region (US, ex-US)
- Duration of the last continuous agalsidase-beta treatment (months). Last treatment refers to patients who had several periods of treatment with agalsidase-beta in the past. In case of several records with a gap ≤ 14 days between the end date and the start date of the following record they are considered as same treatment. The end-date of agalsidase-beta should be taken as the F20 treatment start date (regardless of whether there is an end-date for agalsidase-beta in the database).
- % Residual enzyme activity in leukocyte (defined as the value in leukocyte × 100/83.5, where 83.5 nmol/hr/mg protein is the mean of reference range)
- % Residual enzyme activity in plasma (defined as the value in plasma ×100/12.95, where 12.95 nmol/ hr/mL is the mean of reference range)
- eGFR (estimated using CKD-EPI equation and expressed in ml/min/1.73 m²); See Section 9.1.
- eGFR slope (ml/min/1.73 m²/year) at screening (based on historical serum creatinine and screening serum creatinine measures) as calculated within the EDC system (using linear regression).
- eGFR slope (ml/min/1.73 m²/year) at baseline (based on historical serum creatinine, screening and baseline serum creatinine measures as well as any unscheduled eGFR assessments before baseline visit) and calculated using simple linear regression in a similar way to the approach described in Section 9.3.3.
- Baseline eGFR class (≤ 60 ; $60 < \text{and} \le 90$; $> 90 \text{ mL/min/1.73m}^2$)
- Baseline eGFR slope class (≤ -5 ; > -5 mL/min/1.73m²/year)
- Plasma Lyso-Gb3
- Fabry disease (FD) classification (classic / non-classic) (See Section 7.4 for definition. In case of missing data subjects will not be classified)
- UPCR Categories ($\leq 0.5 \text{ gr/gr}$; 0.5 < and < 1 gr/gr; $\geq 1 \text{ gr/gr}$)
- UPCR Stratification (based on screening values) ($< 1 \text{gr/gr}; \ge 1 \text{ gr/gr}$)
- Treatment with ACEi or ARB (yes/no)
- Premedication use for agalsidase-beta infusion prior to 1st infusion (yes / no)
- ADA status for PRX-102 (positive /negative). The determination of the status is based on the results of the IgG for PRX-102 at baseline (Section 11.7).
- ADA status for agalsidase-beta (positive /negative). The determination of the status is based on the results of the IgG at baseline for agalsidase-beta (Section 11.7).

